### **2-4 Questionnaire tool and data extraction**

Patients' data were collected from medical records (demographics data, medication use history, and clinical profile). Cost data was obtained from the finance department at the center. Financial data included all available direct medical costs, such as treatment and physician visits. Moreover, patients were contacted to estimate the indirect cost associated with breast cancer therapy. A validated assessment tool, the Generalized Anxiety Disorder 7-item (GAD-7) and the Patient Health Questionnaire (PHQ-9) were used to assess anxiety and depression [Spitzer et al., 2006; Kroenke et al., 2001]. The patients were asked to determine the degree of applicability of each item (question) on a 4-point Likert scale. The participants' responses varied from 0 to 3, with 0 denoting "Not at all" and 3 denoting "Nearly every day." Nine elements comprise the PHQ-9 instrument. Items are scored on a scale of 0 to 3, resulting in a total score that ranges from 0 to 27. A total score of 0–4 indicates minimal depression, 5–9 mild depression, 10–14 moderate depression, 15–19 moderately severe depression, and 20–27 severe depression. Seven elements comprise the

GAD-7 instrument. Items are scored on a scale of 0 to 3, resulting in a total score that ranges from 0 to 21. Mild anxiety is indicated by a total score of 5–9, moderate anxiety by 10–14, and severe anxiety by 15–21.

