## **2-6 Data Analysis**

Data was analyzed using IBM SPSS Statistics version 26. Descriptive statistics (mean, standard deviation, frequency, and percentage) were used to summarize demographic and clinical variables. The Kolmogorov-Smirnov test was applied to assess the normality of continuous variables, and due to non-normal distribution, non-parametric tests were used.

Bivariate analyses included Spearman's correlation coefficient to evaluate associations between psychological outcomes (depression, anxiety, stress) and continuous predictors such as sleep quality, cost, and number of children. The Kruskal-Wallis H test was employed to examine differences in distress levels across cancer stages.

Categorical associations were evaluated using Pearson's Chi-square test. Binary logistic regression analysis was conducted to identify predictors of severe anxiety. Additionally, multivariate linear regression models were constructed for each psychological outcome (PHQ-9, GAD-7, stress), and multicollinearity was assessed using the Variance Inflation Factor(VIF).

Receiver Operating Characteristic (ROC) curve analysis was used to assess the predictive accuracy of stress scores for severe anxiety, with Area Under the Curve (AUC) interpreted based on conventional thresholds. Conceptual path modeling was used to explore potential indirect relationships between stress and anxiety, mediated by sleep disturbance and impaired daily performance.

All tests were two-tailed, and a p-value of less than 0.05 was considered statistically significant.

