### 3 - Results

A total of 500 breast cancer patients were included in the final analysis. Descriptive statistics revealed a high prevalence of psychological distress within the sample, with elevated scores in depression, anxiety, and stress domains.

Spearman correlation analysis revealed strong positive associations between sleep difficulty and psychological outcomes: depression ( $r = 0.85$ ), anxiety ( $r = 0.77$ ), and stress ( $r = 0.85$ ), all statistically significant at  $p < 0.001$ . Use of sedatives was also significantly correlated with elevated distress scores ( $r > 0.90$  across models).

Kruskal-Wallis tests demonstrated statistically significant differences in mean ranks of depression, anxiety, and stress across cancer stages ( $p < 0.01$ ), with higher distress in patients with advanced-stage disease.

Multivariate linear regression identified the following as significant predictors of psychological distress:

- PHQ9\_Total:  $\beta = 0.42$ ,  $p < 0.001$
- Anger:  $\beta = 2.08$ ,  $p < 0.001$
- Cancer Stage:  $\beta = 0.92$ ,  $p = 0.0014$

Psychological support was not a significant predictor ( $p = 0.606$ ).

Binary logistic regression showed that PHQ9 and anger significantly predicted severe anxiety, with odds ratios of 1.32 and 1.27, respectively ( $p < 0.001$ ). Stage of disease also emerged as a significant factor in anxiety prediction.

Receiver Operating Characteristic (ROC) curve analysis yielded an Area Under the Curve (AUC) of 0.74 for stress in predicting severe anxiety, indicating a fair level of discriminative ability.

Finally, conceptual path analysis demonstrated that the relationship between stress and anxiety was primarily indirect, mediated through sleep disturbance and daily performance impairment. The direct path from stress to anxiety was negligible ( $r = -0.01$ ), suggesting a mediated mechanism of action.

**Table 1.** Descriptive Statistics of Study Variables

Variable	N	Minimum	Maximum	Mean	SD
Total Cost	500	80	34785	3721.69	4456.79
PHQ9_Total	500	1	27	17.99	6.11
GAD7_Total	500	1	21	12.79	3.81
Cancer Stage	500	0	4	2.52	1.09
Children	500	0	5	2.53	1.63
Metastatic	500	0	1	0.36	0.48
Stress Level	500	0	4	2.64	0.79

The descriptive characteristics of the study variables are presented in **Table 1**. Depression and anxiety scores were moderately high, while stress levels were also elevated. Treatment cost showed substantial variability across participants.

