Although anger remains an underexplored emotional construct in oncology, its relevance is gaining traction. In Iraq, sociocultural norms that discourage emotional expression, combined with the psychological toll of cancer, may intensify internalized anger, contributing to emotional dysregulation. This perspective is supported by findings from the national report, which highlighted elevated psychological distress among cancer patients and emphasized the role of suppressed emotions in shaping anxiety and avoidance behaviors (20).

These findings emphasize the significance of addressing emotional dysregulation, particularly in patients presenting with overlapping symptoms of depression and anxiety.

This suggests that psychological screening tools should incorporate anger-related items to facilitate the early identification of high-risk cases.

The conceptual path model derived from the dataset suggests that stress influences anxiety primarily through indirect mechanisms, notably sleep disturbance and impaired daily functioning. While the direct association between stress and anxiety was minimal ( $r = -0.01$ ), robust indirect effects were observed via sleep problems ( $r = 0.74$ ) and functional impairment ( $r = 0.77$ ). These findings are consistent with regional studies from Egypt and Oman, highlighting sleep disturbance and fatigue as key mediators of psychological distress in oncology patients. (Al-Habsi et al., 2021; Gabra & Hashem, 2021; Hendy et al., 2025).

This structure reinforces theoretical frameworks such as the Transactional Model of Stress and Coping, where maladaptive emotional responses (e.g., stress) translate into clinical outcomes (e.g., anxiety) through sleep and functional capacity mediators. Similar models have been proposed in Jordanian studies (24). Though the present model uniquely incorporates performance and anger as variables of interest, adding depth to the psychosocial profile.

The inclusion of psychological support and its weak inverse association with anxiety ( $r = -0.07$ ) further suggests that strengthening emotional resources could buffer the transition from stress to anxiety. This model may therefore serve as a foundational structure for targeted interventions in Iraqi cancer care systems, particularly in resource-limited settings.

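### The conclusion that stress acts on anxiety partly through daily performance impairment has no valid indirect effect behind it in the text or tables, and the 0.74 and 0.77 offered as indirect effects cannot be that

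*Combined protocol and SAP*

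**What the plan says.** Section 2-6 (Data Analysis) announces a conceptual path model for possible indirect links between stress and anxiety, "mediated by sleep disturbance and impaired daily performance". The Results report the outcome as demonstrated: the relationship is primarily indirect, "mediated through sleep disturbance and daily performance impairment". They add: "The direct path from stress to anxiety was negligible ( $r = -0.01").

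The text under Figure 3 repeats the two mediators, calling the second one impaired daily functioning. It says that the figure carries β coefficients. The Discussion states that "robust indirect effects were observed via sleep problems", with r = 0.74, and in the same sentence gives r = 0.77 for functional impairment. It presents performance as one of the variables that set this model apart and offers the model as a basis for interventions.

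On measurement, section 2-4 names two instruments: "GAD-7) and the Patient Health Questionnaire (PHQ-9) were used to assess anxiety and depression". The other sources are medical records for demographic, medication and clinical data, the finance department for direct costs, and patient contact for indirect costs. No item, scale or scoring is given for daily performance. No row in Tables 1 to 6 carries it under any of its names.

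**The concern.** The study draws a positive conclusion about two mediators. For the sleep mediator, a reader can at least test the claim roughly, because Table 2 gives its correlations with stress and with GAD-7. For daily performance the only number in the text is 0.77, and it is not stated which path that number describes. If 0.77 is not an indirect effect, the text and tables report no estimate of mediation through daily performance. Interventions aimed at daily functioning would then rest on an unreported quantity.

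**Working it through.** **Inputs**
- Table 2 (Spearman): stress with GAD-7, 0.65; stress with sleep difficulty, 0.85; sleep difficulty with GAD-7, 0.77.
- Results and Discussion: direct path -0.01.
- Discussion: 0.74 via sleep problems and 0.77 via functional impairment, both described as indirect effects.

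Throughout, Spearman values are treated as standardised correlations, and Sleep Difficulty is taken as the sleep mediator in steps 1 and 3.

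**Step 1. Can the stated direct path be reproduced?** The partial correlation of stress and GAD-7 given sleep difficulty alone is

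(0.65 - 0.85 × 0.77) / √[(1 - 0.85²)(1 - 0.77²)] = -0.013

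The range is -0.054 to +0.025 over rounding of the three inputs. The stated -0.01 is compatible with this.

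**Step 2. Can 0.74 and 0.77 be indirect effects?** In a standardised linear model, total = direct + sum of indirect effects.
- Reported parts: -0.01 + 0.74 + 0.77 = 1.50.
- Rounding moves this by at most 3 × 0.005 = 0.015, so it lies between 1.485 and 1.515.
- Total from Table 2: 0.65 (0.645 to 0.655 with rounding).
- With a direct path of -0.01, the indirect effects should sum to 0.65 + 0.01 = 0.66. The two reported values sum to 1.51, about 2.3 times that.
- Each value alone already exceeds 0.65. An indirect effect can exceed the total when the direct path is clearly negative, but here it is only -0.01.
- Another indirect path could close the gap only if it were about 0.65 - 1.50 = -0.85. The documents describe no such path.

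**Step 3. Does the near-zero direct path need a second mediator?** With sleep difficulty as the only mediator:
- sleep-to-anxiety coefficient: (0.77 - 0.65 × 0.85) / (1 - 0.85²) = 0.784
- indirect effect: 0.85 × 0.784 = 0.666
- direct path: 0.65 - 0.666 = -0.016 (rounding range -0.066 to +0.030)

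A model without daily performance already gives a direct path near zero.

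**Step 4. Does step 3 rule out a second mediator?** No. Keep the three Table 2 values and take 0.77 as the correlation of performance with GAD-7. The other performance correlations below are assumptions; the documents do not give them. Both sets form valid correlation matrices.

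| Assumed stress-performance | Assumed sleep-performance | Direct | Indirect via sleep | Indirect via performance |
|---|---|---|---|---|
| 0.65 | 0.75 | -0.04 | 0.40 | 0.29 |
| 0.74 | 0.85 | -0.04 | 0.38 | 0.31 |

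In both, the three parts add to 0.65. An indirect effect of about 0.3 through performance is therefore compatible with Table 2, and so is none.

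**The case against.** The strongest reply is that this is a reporting gap in an exploratory analysis. Section 2-6 calls the model conceptual and speaks of potential relationships. A coefficient is quoted for functional impairment. Figure 3, said to carry β coefficients, is not available in the text reviewed and cannot be counted against the study. Nor is daily performance alone in lacking a described instrument: section 2-4 describes none for stress, sleep or anger either. The sleep-only calculation may also not use the authors' sleep variable, since 0.74 matches neither Sleep Difficulty correlation used here, and other sleep variables appear in Tables 2 and 4.

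Much of this stands, and it rules out several stronger readings that a reader might infer:
- *That daily performance was never measured.* A coefficient is reported, so some variable may well exist. What can be said is that it is not defined or tabulated.
- *That sleep leaves the second path nothing to explain.* Step 4 shows otherwise.
- *That the variable shares items with the anxiety scale.* Nothing says how it was built. Items from GAD-7 would overlap the outcome; items from PHQ-9 would overlap depression instead.
- *That half of the mediation is unsupported.* It is one of two named mediators, not a computed share.

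The reply does not reach step 2. The additivity check does not depend on which sleep variable was used or on what the figure shows. The Results also say that mediation was demonstrated, which goes beyond exploration.

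**Conclusion.** The point holds in this form: the text and tables report no valid indirect effect through daily performance, and 0.74 and 0.77 are mislabelled. Read as indirect effects, they and the direct path add to 1.50 against a total of 0.65, a gap that rounding cannot close. They are more likely single-path or bivariate correlations. The reported direct path of -0.01 is not evidence for a second mediator, because sleep difficulty alone gives about -0.02, but it is not evidence against one either.

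This rests on a linear standardised model, on Spearman values standing in for standardised correlations, on the stress-GAD-7 correlation being the total effect, and on Table 2 as printed. The close match in step 1 does not prove that the authors fitted a sleep-only model. The prevalence and regression results are not affected; the mediation conclusion is, and it should be corrected before it is used.

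**What to change.** 1. In section 2-4, state how daily performance was asked and scored, and whether any GAD-7 or PHQ-9 item enters it. Use one name for it throughout. Describe the stress, sleep and anger measures in the same place.
2. Add daily performance to Tables 1 and 2.
3. Fit stress, sleep and daily performance together in one model for GAD-7. Report the direct path and a product-of-coefficient indirect effect for each mediator, with bootstrap intervals.
4. Put these in place of 0.74 and 0.77 as the indirect effects. If those two values are kept, label them as the path or bivariate correlations they are, naming the two variables each one links.
5. Keep the daily-performance claim in the Results, the Figure 3 text and the Discussion only if its interval excludes zero and the variable is not built from GAD-7 items. Otherwise remove it.

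The cost is one refit on data already held, plus edited wording. The downside is that one of the two claimed mediators may be lost. The refit will not establish time order, since section 2-1 describes a cross-sectional study.

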**Table 2.** Spearman Correlation Matrix Among Study Variables

Variable	PHQ9_Total	GAD7_Total	Stress Level	Sleep Difficulty	Sleep Satisfaction	Total Cost

PHQ9_Total	1.00	0.79	0.66	0.85	0.49	-0.11
GAD7_Total	0.79	1.00	0.65	0.77	0.62	-0.10
Stress Level	0.66	0.65	1.00	0.85	0.55	-0.12
Sleep Difficulty	0.85	0.77	0.85	1.00	0.48	-0.08
Sleep Satisfaction	0.49	0.62	0.55	0.48	1.00	-0.09
Total Cost	-0.11	-0.10	-0.12	-0.08	-0.09	1.00

[figure not shown]
Spearman correlation coefficients between psychological outcomes and sleep-related variables are shown in **Table 2**. Strong positive correlations were observed between depression, anxiety, stress, and sleep difficulty.

**Table 3.** Kruskal–Wallis Test for Differences Across Cancer Stages

Variable	Chi-square (H)	df	P-value
Stress Level	31.092	3	<0.001
PHQ9_Total	14.762	3	0.002
GAD7_Total	19.705	3	<0.001

The Kruskal–Wallis test results (**Table 3**) indicate significant differences in depression, anxiety, and stress levels across cancer stages ( $P < 0.05$ ).

**Figure 1.** Chi-square (H) Values for Stress, Depression, and Anxiety

**Figure 1** shows the Chi-square (H) values for stress, depression, and anxiety. Stress exhibited the highest value (H = 31.09), followed by anxiety (H = 19.71) and depression (H = 14.76), all indicating significant differences across groups ( $P < 0.05$ ).

**Table 4.** Multiple Regression Analysis of Factors Associated with Depression, Anxiety, and Stress among Patients

Outcome	Predictor	B	T	P-value	VIF	R 
Depression (PHQ-9)	Use of Sedatives	4.842	10.817	<0.001	1.766	0.702
	Sleep Difficulty	4.52	11.221	<0.001	4.866	
	Sleep Satisfaction	0.364	2.01	0.045	1.021	
	Children	0.075	0.626	0.532	1.039	
	Total Cost	7.5E-5	2.209	0.028	1.022	

	Metastatic	-0.13	-0.408	0.684	1.048	
Anxiety (GAD7)	Use of Sedatives	4.064	12.807	<0.001	1.766	0.615
	Sleep-related Worry	1.521	6.193	<0.001	3.655	
	Sleep Satisfaction	0.539	1.886	0.060	4.866	
	Children	0.205	1.889	0.060	1.039	
	Total Cost	3.0E-5	1.246	0.213	1.022	
	Metastatic	0.203	0.896	0.371	1.048	
Stress Level	Use of Sedatives	1.856	29.413	<0.001	1.766	—
	Sleep-related Worry	0.149	3.048	0.002	3.655	
	Children	0.037	1.705	0.089	1.039	
	Metastatic	0.084	1.865	0.063	1.048	
	Total Cost	3.4E-6	0.711	0.477	1.022	

The results of the multiple regression analysis are summarized in **Table 4**. Use of sedatives and sleep-related worry were significant predictors of stress, depression, and anxiety scores.

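### Sleep Satisfaction figures conflict between Table 2 and Table 4 and within Table 4; the anxiety-block row under that label is very probably Sleep Difficulty and must be checked against the SPSS output

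*Combined protocol and SAP*

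**What the plan says.** Section 2-6 (Data Analysis) plans Spearman correlations and one multivariable linear model per outcome (PHQ-9, GAD-7, stress), and says that "multicollinearity was assessed using the Variance Inflation Factor(VIF". Section 3 (Results) reports them as follows.

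- **Table 2 (Spearman)**, introduced with "Spearman correlation coefficients between psychological outcomes and sleep-related variables are shown in". The Sleep Satisfaction row reads "Sleep Satisfaction 0.49 0.62 0.55 0.48 1.00 -0.09". In column order, these are its correlations with PHQ-9, GAD-7, Stress Level, Sleep Difficulty, itself and Total Cost.
- **Table 4**, titled "Multiple Regression Analysis of Factors Associated with Depression, Anxiety, and Stress among Patients". The depression block (R² 0.702) prints Sleep Difficulty with B 4.52, t 11.221, VIF 4.866, and Sleep Satisfaction with B 0.364, t 2.01, p 0.045, VIF 1.021. The anxiety block (R² 0.615) prints Sleep-related Worry with B 1.521, t 6.193, VIF 3.655, and a row labelled Sleep Satisfaction with B 0.539, t 1.886, p 0.060, VIF 4.866. The anxiety block has no Sleep Difficulty row.
- **Text below Table 4.** It names sedative use and sleep-related worry as significant for all three outcomes, although the depression block prints no Sleep-related Worry row.

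Nothing in the documents explains the change of VIF under one label, or says how Sleep Satisfaction is coded.

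**The concern.** A VIF depends only on the predictors in a model, not on the outcome. It also sets a ceiling on how strongly a predictor can correlate with any other predictor in that model. Two things therefore look wrong.

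1. A VIF of 1.021 says that Sleep Satisfaction is almost unrelated to everything else in the depression model, including Sleep Difficulty. Table 2 says that the two are moderately correlated.
2. The same label has VIF 1.021 in one block and 4.866 in the next, while the other repeated predictors do not move. The value 4.866 is the one printed for Sleep Difficulty.

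At stake is whether a reader can tell which sleep variable each adjusted coefficient belongs to. If the anxiety row is mislabelled, the adjusted result for Sleep Difficulty on GAD-7 is shown under another name and the Sleep Satisfaction result is absent. The text meanwhile gives prominence to the unadjusted Sleep Difficulty correlation of 0.77 with anxiety.

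**Working it through.** **Inputs.** From section 3: "A total of 500 breast cancer patients were included in the final analysis" (n = 500). From Table 1: "PHQ9_Total 500 1 27 17.99 6.11" and "GAD7_Total 500 1 21 12.79 3.81", so the outcome SDs are 6.11 and 3.81. B, t, VIF and R² are from Table 4; correlations are from Table 2. From section 2-6: "All tests were two-tailed, and a p-value of less than 0.05 was considered statistically significant".

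**Step 1: reproduce the printed p-values.** With 492 or 493 degrees of freedom (7 or 6 predictors), t = 2.01 gives two-sided p = 0.045 and t = 1.886 gives p = 0.060. Both match, so t and p agree in both disputed rows.

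**Step 2: Table 2 against the depression-block VIF.** VIF = 1/(1 − R_j²), where R_j² is from regressing that predictor on the others.
- VIF 1.021 gives R_j² = 1 − 1/1.021 = 0.0206, so |r| with any other predictor is at most √0.0206 = 0.143.
- r = 0.48 would need VIF of at least 1/(1 − 0.48²) = 1.30. Converting Spearman to Pearson under normality, 2·sin(π·0.48/6) = 0.497, raises this to 1.33.

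**Step 3: ceiling on the correlation with PHQ-9.** The standardised coefficient is t·√((1 − R²)·VIF/df) = 2.01·√(0.298·1.021/492) = 0.050. The remaining predictors contribute at most 0.143·q. Here q is the SD of their part of the fit in outcome-SD units, from q² + 2·0.050·0.143·q + 0.050² = 0.702, so q = 0.829. The ceiling is 0.050 + 0.143·0.829 = 0.17. Table 2 prints 0.49.

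**Step 4: do the blocks share one predictor set?** Sedatives (1.766), Children (1.039), Total Cost (1.022) and Metastatic (1.048) have the same VIF in all three blocks, and Sleep-related Worry (3.655) has the same VIF in the two blocks that print it. That points to one common model with only some rows printed. In that case SE = B/t for a given predictor should change between blocks only by the ratio of residual SDs:
- depression: 6.11·√(0.298·499/492) = 3.359
- anxiety: 3.81·√(0.385·499/492) = 2.381
- expected SE ratio: 2.381/3.359 = 0.709

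**Step 5: observed SE ratios, anxiety over depression.**

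| Rows compared | SEs | Ratio |
|---|---|---|
| Sedatives | 0.3173 / 0.4476 | 0.709 |
| Total Cost | 2.408E-5 / 3.395E-5 | 0.709 |
| Metastatic | 0.2266 / 0.3186 | 0.711 |
| Disputed row / depression Sleep Satisfaction | 0.2858 / 0.1811 | 1.578 |
| Disputed row / depression Sleep Difficulty | 0.2858 / 0.4028 | 0.709 |
| Children | 0.1085 / 0.1198 | 0.906 |

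The disputed row fits Sleep Difficulty on both VIF and SE. As Sleep Satisfaction its SE should be about 0.1811·0.709 = 0.128, not 0.286.

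**Step 6: implied predictor SD,** s·√VIF/(SE·√499), with s the residual SD.
- Total Cost: 4477 and 4475 in the two blocks, against 4456.79 in Table 1 (fits).
- Metastatic: 0.483 and 0.482, against 0.48 (fits).
- Children: 1.28 and 1.00, against 1.63 (does not fit).
- Sleep rows: 0.823 for Sleep Difficulty, 0.823 for the disputed row, 0.839 for depression-block Sleep Satisfaction, 0.830 for Sleep-related Worry. These are too close together to separate the labels, so VIF and SE carry the argument.

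**The case against.** **Coding direction or type of correlation.** Reverse scoring changes a sign, not a VIF, and the ceilings above are on absolute values. Table 2 uses ranks while VIF uses Pearson correlations, but that difference does not plausibly take 0.48 down to 0.143 or less.

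**The check is imperfect.** Children fails it: its SE ratio is 0.906 and its implied SD misses Table 1 in both blocks. This stands. The implied-SD method matches only two of the three predictors that can be tested against Table 1. It does not rescue the disputed row, because Sedatives, Total Cost and Metastatic pass and the VIF match does not use standard errors. It does mean that more than one row of Table 4 needs checking.

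**Which label is wrong is not settled.** This also stands. Step 2 casts doubt on the depression-block Sleep Satisfaction row too, and a VIF of 4.866 is compatible with Table 2's 0.48. A plain swap of the two depression labels does not help, however. Sleep Difficulty would then have VIF 1.021 and a correlation with PHQ-9 of at most 0.17, against 0.85 in Table 2. The large depression coefficient (4.52) also favours Sleep Difficulty for the 4.866 row. Only the SPSS output can confirm it.

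**Stronger readings that the documents do not support.** A reader might infer that the paper misreports which sleep variable is related to anxiety, or that its mediation claim falls. The significant sleep term in the anxiety block is Sleep-related Worry (p < 0.001), whose VIF and SE are consistent between the anxiety and stress blocks (SE ratio 0.199, the same as Sedatives). The disputed row has p = 0.060 under either label. The 0.77 is openly reported as a bivariate correlation, and a non-significant adjusted coefficient does not contradict it. The mediator is described as sleep disturbance or sleep problems and is never equated with Sleep Difficulty.

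**Conclusion.** The inconsistency is real and follows from the printed figures. Table 2's 0.48 and 0.49 cannot stand with a VIF of 1.021, which allows about 0.14 and 0.17. One label also carries VIFs of 1.021 and 4.866 in what appears to be a common predictor set. At least one label or data column is wrong.

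The disputed anxiety row and the depression-block Sleep Difficulty row are very probably one variable, most likely Sleep Difficulty. This rests on the blocks sharing one predictor set, which the identical VIFs and three of the four SE ratios for predictors shared by both blocks support. Whether Table 2's Sleep Satisfaction column or the 1.021 row is at fault cannot be decided from the documents.

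The effect on conclusions is limited. No significance call changes. What is lost is disclosure: a non-significant adjusted Sleep Difficulty result for GAD-7 (B = 0.539, p = 0.060) is probably hidden, and the adjusted Sleep Satisfaction result for anxiety is probably missing. With VIF 4.866, p = 0.060 is not evidence of no association. The tables still need correcting, because they cannot all be true as printed.

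**What to change.** 1. Check every row of Table 4, including Children, and the Sleep Satisfaction column of Table 2 against the SPSS regression and correlation output. Confirm that the same data column was used in both.
2. Correct whichever label or column is wrong, and state the direction in which Sleep Satisfaction is coded.
3. Print the full common predictor set in every block, so that Sleep Difficulty, Sleep Satisfaction and Sleep-related Worry each appear for each outcome.
4. Only if the output confirms that the anxiety row is Sleep Difficulty: relabel it, add the missing Sleep Satisfaction row, and state next to the r = 0.77 in the Results that the adjusted association was not significant (p = 0.060, VIF 4.866). The wider sleep conclusions need no rewording on this ground.

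The cost is a reading of existing output, two corrected tables and, if confirmed, one added sentence. No new data are needed. A re-run is needed only if a wrong data column was used.

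### The claim that distress rises with cancer stage rests on an undirected test with no stage-wise figures, and the four groups it compared are not identified

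*Combined protocol and SAP*

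**What the plan says.** Section 2-6 (Data Analysis) plans one analysis of stage against the distress scores: "The Kruskal-Wallis H test was employed to examine differences in distress levels across cancer stages". It names no trend test and no pairwise comparison. Spearman correlation is planned for other predictors, and stage is not in the Table 2 matrix.

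Table 1 summarises stage as "Cancer Stage 500 0 4 2.52 1.09" (N, minimum, maximum, mean, SD). Section 2-2 admits patients at every stage.

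Table 3 prints H, degrees of freedom and p for each outcome: "Stress Level 31.092 3 <0.001", "PHQ9_Total 14.762 3 0.002" and "GAD7_Total 19.705 3 <0.001". The sentence beneath it says that the results "indicate significant differences in depression, anxiety, and stress levels across cancer stages".

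The directional wording is elsewhere. The opening text of the Results attaches "with higher distress in patients with advanced-stage disease" to the Kruskal-Wallis finding. The Discussion moves from the H values to greater vulnerability in advanced stages. The Conclusion names advanced stage as a key predictor of both anxiety and depression.

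**The concern.** Two things do not fit together.

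First, the Kruskal-Wallis test asks whether at least one group tends to have higher or lower scores than another. It ignores the order of the groups and returns a statistic without a sign. A statement that distress is higher in advanced disease needs either the stage-wise figures or a test that uses the order. The documents print neither. For depression and stress, nothing else fills the gap.

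Second, Kruskal-Wallis degrees of freedom equal the number of groups minus one, so 3 means four groups. A variable running from 0 to 4 can have up to five levels. The reader is not told whether a middle stage is empty, or whether a group was merged or left out.

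Stage is the main clinical factor in the paper, and the Discussion uses it to argue for stage-specific interventions. If the pattern were flat with one unusual stage, or U-shaped, the same Table 3 could result and that argument would lose its support.

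**Working it through.** **1. Reproduce Table 3.** Formula: p = upper tail of the chi-square distribution at H. Inputs: H and df from Table 3. The last two columns use N = 500 from Table 1.

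| Outcome | H | p, df 3 | printed p | p, df 4 | H/(N − 1) | square root |
|---|---|---|---|---|---|---|
| Depression (PHQ-9) | 14.762 | 0.0020 | 0.002 | 0.0052 | 14.762/499 = 0.030 | 0.17 |
| Anxiety (GAD-7) | 19.705 | 0.00020 | <0.001 | 0.00057 | 19.705/499 = 0.039 | 0.20 |
| Stress | 31.092 | 0.00000081 | <0.001 | 0.0000029 | 31.092/499 = 0.062 | 0.25 |

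The printed p-values reproduce at df = 3. The PHQ-9 row is informative: 0.002 fits df = 3 and not df = 4 (0.005). So df = 3 was really used and is not a misprint.

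**2. Can four groups be right?** Table 1 shows that stages 0 and 4 both occur. It does not show that 1, 2 and 3 all do. Searching for whole-number counts with N = 500 that match mean 2.52 and SD 1.09 after rounding gives solutions whichever middle stage is empty. Examples:

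- Stage 1 empty: counts 52, 162, 208, 78 at stages 0, 2, 3, 4. Mean = (324 + 624 + 312)/500 = 2.52.
- Stage 2 empty: counts 38, 82, 342, 38 at stages 0, 1, 3, 4. Mean = (82 + 1,026 + 152)/500 = 2.52.
- Stage 3 empty: counts 13, 35, 292, 160 at stages 0, 1, 2, 4. Mean = (35 + 584 + 640)/500 = 2.518.

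Each gives SD 1.09. So df = 3 is possible with all 500 patients and no merging.

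**3. What the alternatives would do.**

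- A middle stage is empty: df = 3 stands and nothing changes.
- Two stages were merged: splitting them again in the same patients cannot reduce the between-group variation in ranks, so H cannot fall. The df = 4 p-values in the table are then upper limits.
- A stage was dropped: H changes by an amount that cannot be computed, and the test did not use all 500 patients.

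**4. What H says about direction.** H is built from the squared rank sums of the groups, so reversing the stage codes leaves it unchanged. The tie-corrected H/(N − 1) is the share of rank variance explained by stage group, and the squared Spearman correlation of stage with score cannot exceed it. If Table 3 used all 500 patients at their occupied stage levels, that correlation lies between −0.17 and +0.17 for depression, −0.20 and +0.20 for anxiety, and −0.25 and +0.25 for stress. Table 3 alone does not place it within those limits.

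**5. Whether other results settle the direction.**

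- Table 4 has no stage term for any outcome. Its metastatic indicator, adjusted for sedatives and (for depression and anxiety) sleep satisfaction among others, is not significant: depression B = −0.13 (p = 0.684), anxiety 0.203 (p = 0.371), stress 0.084 (p = 0.063).
- Table 5 (severe anxiety) gives stage an odds ratio of 0.61, and the text describes it as protective.
- Table 6 (severe anxiety, labelled as corrected) gives +0.92, an odds ratio of exp(0.92) = 2.51.
- Both logistic models contain PHQ-9 as a predictor, so neither can show how depression varies with stage.
- The opening text of the Results lists +0.92 under linear regression, but the coefficients and p-values there are those of Table 6.

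**The case against.** The strongest reply is that the planned test was carried out and reported. The Results refer to mean ranks, so the authors may well have looked at them, and reading direction from mean ranks after a significant overall test is ordinary practice. On this view the fault is an unprinted column. Part of that stands: the choice of Kruskal-Wallis is not itself an error, and the sentence under Table 3 claims only what the test supports. But the directional sentences are conclusions of the paper, and a reader cannot check them.

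A second reply concerns the degrees of freedom, and it largely stands. A reader might infer that Table 3 should have had df = 4 and that its p-values are too small. The documents do not support that. A range of 0 to 4 does not prove five occupied levels, and each middle stage could be empty. Nor can it be said that a re-run would raise the p-values: H could change too, and they may move either way.

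A third reply is that Table 6 supersedes Table 5. It is labelled as corrected, and the Discussion mentions an adjustment for stage coding. That is a fair reading, although the text also says that Table 6 confirmed Table 5, and the adjustment is not described. In any case both models concern severe anxiety only.

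**Conclusion.** The point holds as a gap between claim and evidence. For depression and stress, the statement that distress is higher in advanced stage rests on an undirected test with no stage-wise figures. For severe anxiety the directional estimates disagree in sign. The Conclusion on depression is the least supported, since no directional estimate of stage on depression is reported anywhere.

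The stage differences are significant but small: stage group explains about 3% to 6% of rank variance. The unidentified four groups are a reporting gap. At the printed H, df = 4 would give 0.0052, 0.00057 and 0.0000029. These values are illustrative only, and all stay below both the 0.05 criterion and the 0.01 quoted in the text.

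A reader might go further and infer that distress does not rise with stage, or that Table 5 shows it falls. The documents do not support that either; the direction is simply not shown. The limits of ±0.17 to ±0.25 assume a tie-corrected H computed on all 500 patients at their occupied stage levels.

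**What to change.** 1. Print n and the median or mean rank of PHQ-9, GAD-7 and stress for each stage.
2. Test the directional claim with an ordered-alternative test: Jonckheere-Terpstra, or the Spearman correlation of stage with each score. Spearman is already in the plan, so stage can be added to Table 2. The stage-wise figures are still needed beside it, because a trend test alone does not show whether the pattern is monotone.
3. State which four groups Table 3 compared and the n in each. If any stage was merged or dropped, re-run on all occupied levels with the matching degrees of freedom.
4. Limit the directional statements in the Results, Discussion and Conclusion, especially for depression, to what the ordered test shows. State the stage coding behind Tables 5 and 6.

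The cost is a few lines of analysis on existing data and one extra table. The p-values may move either way, and some directional wording may have to be softened.
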